12.7. Appendix 7: Standard Discontinuation Criteria

CDISC Submission Value	CDISC Definition
Adverse event	Any untoward medical occurrence in a patient or clinical investigation subject administered a pharmaceutical product and which does not necessarily have a causal relationship with this treatment. An adverse event (AE) can therefore be any unintended sign (including an abnormal laboratory finding), symptom, or disease temporally associated with the use of a medicinal (investigational) product, whether or not related to the medicinal (investigational) product. For further information, see the ICH Guideline for Clinical Safety Data Management: Definitions and Standards for Expedited Reporting. [Modified from ICH E2A] Synonyms: side effect, adverse experience. See also serious adverse event (SAE), serious adverse experience (Clinical Data Interchange Standards Consortium [CDISC] glossary)
Completed	To possess every necessary or normal part or component or step; having come or been brought to a conclusion (National Cancer Institute [NCI])
Death	The absence of life or state of being dead (NCI)
Lack of efficacy	The lack of expected or desired effect related to a therapy (NCI)
Lost to follow-up	The loss or lack of continuation of a subject to follow-up
Non-compliance with study drug	An indication that a subject has not agreed with or followed the instructions related to the study medication (NCI)
Other	Different than the one(s) previously specified or mentioned (NCI)
Physician decision	A position, opinion or judgment reached after consideration by a physician with reference to subject (NCI)
Pregnancy	Pregnancy is the state or condition of having a developing embryo or fetus in the body (uterus), after union of an ovum and spermatozoon, during the period from conception to birth. (NCI)
Protocol deviation	An event or decision that stands in contrast to the guidelines set out by the protocol (NCI)
Screen failure	The potential subject who does not meet one or more criteria required for participation in a trial

Eluxadoline

CDISC Submission Value	CDISC Definition
Site terminated by sponsor	An indication that a clinical study was stopped at a particular site by its sponsor (NCI)
Study terminated by sponsor	An indication that a clinical study was stopped by its sponsor (NCI)
Withdrawal by subject	An indication that a study participant has removed itself from the study (NCI)

[figure not shown]
12.8. Appendix 8: Study Tabular Summary

[figure not shown]
Parameter Group	Parameter	Value
Trial information	Trial Title	3030-401-002: An Open-Label Pilot Study of Eluxadoline in Participants with Irritable Bowel Syndrome with Diarrhea (IBS-D) Who Have Evidence of Bile Acid Malabsorption (BAM)
	Clinical Study Sponsor	Allergan
	Trial Phase Classification	Phase 4
	Trial Indication	IBS-D
	Trial Indication Type	Treatment
	Trial Type	Efficacy Safety
	Trial Length	Up to 11 weeks, which includes: screening period (0-2 weeks), pretreatment period (2-3 weeks), 4-week open-label treatment period and 2-week post-treatment follow-up period.
	Planned Country of Investigational Site	United States
	Planned Number of Participants	24
	FDA-Regulated Device Study Indicator	No
Participant information	FDA-Regulated Drug Study Indicator	No
	Pediatric Study Indicator	No
	Diagnosis Group	Participants with IBS-D who have evidence of BAM
	Healthy Participant Indicator	No
	Planned Minimum Age of Participants	18
	Planned Maximum Age of Participants	65
Treatments	Sex of Participants	Both
	Stable Disease Minimum Duration	A diagnosis of IBS fulfilled for the last 3 months prior to screening with symptom onset at least 6 months before diagnosis as defined by the Rome IV criteria for IBS.
	Investigational Therapy or Treatment	Eluxadoline
	Intervention Type	Drug
	Pharmacological Class of Investigational Therapy	Locally active mixed mu-opioid receptor (μ OR) agonist, kappa-opioid receptor

Parameter Group	Parameter	Value
	(κ OR) agonist, and delta-opioid receptor (δ OR) antagonist.	
	Dose per Administration	100 mg
	Dose Units	100 mg
	Dosing Frequency	BID
	Route of Administration	Oral
	Current Therapy or Treatment	None
	Added on to Existing Treatments	No
	Control Type	N/A
	Comparative Treatment Name	N/A
Trial design	Study Type	Interventional
	Intervention Model	Open-Label, pilot
	Planned Number of Arms	1
	Planned Number of Cohorts	2
	Trial is Randomized	No
	Randomization Quotient	N/A
	Trial Blinding Schema	None
	Stratification Factor	With and without evidence of BAM
	Adaptive Design	No
	Study Stop Rules	
Participants must prematurely discontinue study treatment for reasons of safety including:
 
 • an SAE considered by the investigator or the sponsor to be possibly related or related to investigational product, • an AE of special interest (SO spasm, pancreatitis, severe constipation) • pregnancy • signs of drug-induced liver injury (DILI) outlined in Appendix 6 Section 12.6, Liver Safety 
Participants may prematurely discontinue study treatment for reasons of safety including:
 
 • the presence of intentional overdose or intentional misuse per investigator discretion,

[figure not shown]
Parameter Group	Parameter	Value
		
 • an AE indicative of a CNS opioid effect, eg, pinpoint pupils, loss of consciousness, delirium, sedation or somnolence, euphoric, anxious or depressed mood, that in the opinion of the investigator or the sponsor is possibly related or related to the investigational product, • a vital sign, and/or laboratory abnormality judged to be clinically significant by the investigator and that in the opinion of the investigator or the sponsor is possibly related or related to the investigational product, • an intolerable AE (defined as an AE that subjectively would cause a participant to consider study withdrawal), • an absence of bowel movements for ≥ 3 consecutive days, based on responses recorded via eDiary, • the use of an excessive amount of loperamide rescue medication, • the occurrence of any other AE that in the opinion of the investigator or the sponsor is possibly related or related to the study treatment that represents a clinically significant safety risk to the participant.

Eluxadoline

[figure not shown]

[figure not shown]
Eluxadoline

Eluxadoline

Eluxadoline

12.10. Appendix 10: Summary Adapted from Guidelines of the US Multi-society Task Force on Colorectal Cancer and Other Colonoscopy Requirements

Note: Participant may be enrolled if no follow-up colonoscopy after polyp removal is due while participating in the study.

1. Participants age 50 years (40 years if African American) and older must have had a colonoscopy with negative findings within the 10 years prior to the screening visit (Visit 1).
2. If the most recent colonoscopy revealed hyperplastic polyps that were entirely removed, the participant may be enrolled, provided the colonoscopy was performed within 10 years prior to the screening visit (Visit 1).
3. If the most recent colonoscopy revealed 2 or fewer small (< 1 cm) adenomatous polyps with tubular structure with low grade dysplasia and without appreciable villous tissue, the participant may be enrolled, provided the colonoscopy was performed within 5 years prior to the screening visit (Visit 1).
4. Participants who have 1 first-degree relative with colorectal cancer or adenomatous polyps diagnosed before age 60 or 2 first-degree relatives with colorectal cancer diagnosed at any age, must have had a colonoscopy with negative findings 5 years before the screening visit (Visit 1). This applies to participants who are 40 years or older and to participants younger than 40 years, who are 10 or fewer years from the age at which their youngest relative was found to have 1 of the aforementioned conditions.
5. Participants who have 1 first-degree relative with colorectal cancer or adenomatous polyps diagnosed at age 60 or older or 2 second-degree relatives with colorectal cancer diagnosed at any age, must have had a colonoscopy with negative findings within 10 years prior to the screening visit (Visit 1). This applies to participants who are 40 years or older and to participants younger than 40 years, who are 10 or fewer years from the age at which their youngest relative was found to have 1 of the aforementioned conditions.

Other Colonoscopy Requirements:

Participants of any age who have alarm symptoms must have had a colonoscopy with negative findings after the onset of the alarm symptoms and within 5 years prior to the screening visit (Visit 1). Alarm symptoms include lower GI bleeding (rectal bleeding or heme-positive stool), iron-deficiency anemia, and weight loss. (Note: Current unexplained or clinically significant alarm symptoms are exclusionary.) These requirements are adapted based on recent Guidance on Colorectal Cancer Screening ([Levin 2008](#); [Lieberman 2012](#); [Qaseem 2012](#)).

[figure not shown]
References

12.11. Appendix 11: Bristol Stool Form Scale (BSFS)

[figure not shown]
Eluxadoline

[figure not shown]

[figure not shown]
Eluxadoline

[figure not shown]
Eluxadoline

[figure not shown]
Eluxadoline

Eluxadoline

Eluxadoline

Eluxadoline

12.13. Protocol Amendment 1 Summary

Section No. and Name	Description of Change	Brief Rationale
Section 1 Synopsis (Study design table); Section 2 SOA; Section 5.1 Table 5-1	
Addition of bolded text to footnote (footnote a in synopsis and footnote b in SOA):
 
Screening and Pretreatment periods may be combined, if results of fasting serum 7αC4 test or 48-hour fecal BA collection conducted within 1 calendar year from Screening Visit are available at the time of the combined visit or results from fasting serum 7αC4 test are available prior to the start of study treatment.
	
Section 9 Screening Visit 1	
Addition of bolded text: This visit may be combined with the pretreatment visit if results from a fasting serum 7αC4 test or 48-hour fecal BA collection, conducted within 1 calendar year prior to screening, are available at the time of the combined visit or results from fasting serum 7αC4 test are available prior to the start of study treatment. The screening visit will occur approximately 2 to 3 weeks before the first dose of study drug (if combined with pretreatment visit) and no more than 5 weeks before the first dose of study drug, if the participant requires an additional week for each, screening and pretreatment procedures).
	
The original protocol allowed screening and pretreatment visits to be combined for participant who had historical results of fasting serum 7αC4 test or 48-hour fecal BA collection available within 1 calendar year from screening. The turnaround for 7αC4 results used to be approximately 2-3 weeks. The 7αC4 test results are now available in approximately 1 week which was a trigger to allow combining Screening and Pretreatment for all study participants. This will allow fewer visits for some participants, decreasing the participant burden.

Section 9 Pretreatment (Visit 2)	
Addition of bolded text: This visit may be combined with the screening visit if results from a fasting serum 7αC4 test or 48-hour fecal BA collection, conducted within 1 calendar year prior to screening, are available at the time of the combined visit or results from fasting serum 7αC4 test are available prior to the start of study treatment.
	

Section No. and Name	Description of Change	Brief Rationale
Section 5.1	Duration of screening period changed to 40-2 weeks and defined as Week - 3 to -45 prior to Baseline Visit (V3, Study Day 1)	To correct inaccuracy in original protocol
Section 7.5	Addition of bolded text describing destruction of test material: The study site must send any unused study treatment to the vendor specified, for destruction or have study drug destroyed per documented institutional standards of practice that have been approved by the sponsor.	Due to DEA handling restrictions and institution processes the site is unable to return unused study drug to sponsor. The alternative destruction process was agreed upon and documented in Note to file
Section 9.8.2.1 AEs of Special Interest	Addition of bolded text for clarification: Once notified, the investigator must contact the participant to review the participant's status as soon as possible (eg, within 24 hours), to assess the severity of his/her constipation or the presence of any sequelae of constipation. Every attempt should be made to reach the study participant within 24 hours.	For clarity: Severe constipation is an adverse event of special interest and due to the potential seriousness of this condition, investigator's should attempt to reach the participant within a 24 hour period. The previous iteration of this text allow for interpretation of the phrase "as soon as possible", while the amendment makes it clear that "Every attempt should be made to reach the study participant within 24 hours".
Section 12.9 Appendix 9	The sponsor contact information was updated.	Personnel change at Allergan

4.0 INTRODUCTION

[figure not shown]
This statistical analysis plan (SAP) provides a more technical and detailed elaboration of the statistical analyses of the efficacy and safety data as outlined and/or specified in the final protocol of Study 3030-401-002 dated 19 Oct 2017 and the most recent amendment dated 17 Apr 2019. Specifications of tables, figures, and data listings are contained in a separate document. The SAP for pharmacokinetic will be prepared separately.

Study 3030-401-002 is a Phase 4, non-randomized, open-label, parallel-group, cohort controlled trial to evaluate the efficacy, safety, tolerability and pharmacokinetics of eluxadoline in participants meeting the Rome IV criteria for IBS-D with and without evidence of BAM. This study will be comprised of a 0 to 2-week screening period, a 2 to 3-week pretreatment period, a 4-week open-label treatment period during which time participants will receive eluxadoline 100 mg BID, and a 2-week post-treatment safety follow-up.

[figure not shown]
There will be 24 participants enrolled in the study, 12 with evidence of BAM and 12 without evidence of BAM. Cohort 1 consists of IBS-D participants with evidence of BAM treated with eluxadoline 100 mg oral tablets BID with food. Cohort 2 consists of IBS-D participants without evidence of BAM treated with eluxadoline 100 mg oral tablets BID with food. The 100 mg BID dose selected for this trial is consistent with US and global labeling for eluxadoline in IBS-D. This non-randomized design is considered most appropriate since the cohort assignment will be based on the determination of BAM status. As far as possible, the 2 cohorts will be matched by age, gender and severity of historic symptoms based on the investigator's discretion.

[figure not shown]
The total duration of the study is up to 11 weeks, which includes: screening period (1-2 weeks), pretreatment period (2-3 weeks), 4-week open-label treatment period, and 2-week post-treatment follow-up period. A total of 6 study visits are planned for each participant: Screening, Week -3 to -4 (Visit 1); Pretreatment, Week -3 to -2 (Visit 2); Day 1 (Visit 3; first administration of study drug); Week 2 (Visit 4; Week 2 of treatment), may be done by telephone; Week 4 (Visit 5; end of treatment/early termination); Week 6 (Visit 6; post-treatment follow-up), may be done by telephone. The end of the study is defined as the date of Visit 6. The schedule of evaluations for Study 3030-401-002 is presented in Table 4-1.

Table 4-1: Schedule of Activities (SoA)

Activity	Start Date	End Date	Duration	Responsible Person
Initial market research	2023-01-01	2023-01-15	14 days	Market Research Team
Product development	2023-02-01	2023-05-31	110 days	Product Development Team
Regulatory filing	2023-06-01	2023-07-15	45 days	Regulatory Affairs Team
Manufacturing setup	2023-08-01	2023-09-30	60 days	Manufacturing Team
Marketing campaign	2023-10-01	2023-12-31	90 days	Marketing Team
Post-launch monitoring	2024-01-01	Ongoing	Ongoing	Product Safety Team

5.0 OBJECTIVES

The primary objectives of this study are to evaluate the efficacy of eluxadoline 100 mg BID in IBS-D participants with evidence of BAM compared to IBS-D participants without evidence of BAM and to evaluate the safety and tolerability of eluxadoline 100 mg BID in IBS-D participants with evidence of BAM and in IBS-D participants without evidence of BAM. The secondary objectives of this study are to further evaluate the efficacy of eluxadoline 100 mg BID in IBS-D participants with evidence of BAM compared to IBS-D participants without evidence of BAM and to evaluate the population PK of eluxadoline in IBS-D participants with and without evidence of BAM.

6.0 PARTICIPANT POPULATIONS

The analysis populations will consist of participants as defined below.

6.1 SCREENED POPULATION

All screened participants who sign informed consent.

6.2 ENROLLED POPULATION

All participants in Screened Population who meet the eligibility criteria and enter the open-label treatment period (on Day 1, Visit 3).

6.3 MODIFIED INTENT-TO-TREAT POPULATION

All participants in Enrolled Population with ≥ 1 postbaseline assessment for Bristol Stool Form Scale (BSFS).

6.4 SAFETY POPULATION

All participants who received ≥ 1 dose of study treatment.

7.0 PARTICIPANT DISPOSITION

The number of participants in 3 study populations (Enrolled, mITT, and Safety) will be summarized overall, by participant group (BAM or Non-BAM) and overall for the Screened Population.

The number of screen failures (ie, participants who enter the Screening Period and the Pretreatment but not enter the open-label treatment period (on Day 1, Visit 3)) and participants ineligible for enrollment, along with the associated reasons for failure, will be tabulated overall. Screened participants who are not enrolled will also be listed with the reasons for exclusion.

The number and percentage of participants who complete the open-label Treatment Period and Post-treatment Period and of participants who prematurely discontinue during the same period will be presented by participant group and overall for Enrolled Population. The reasons for premature discontinuation from the open-label study period or Post-treatment Period as recorded in the eCRF will be summarized (number and percentage) by participant group for the Enrolled Population. All participants who prematurely discontinue during the open-label Treatment Period or Post-treatment Period will be listed by discontinuation reason for the Enrolled Population.

8.0 DEMOGRAPHICS AND OTHER BASELINE CHARACTERISTICS

Demographic parameters (age; sex; race; ethnicity), baseline characteristics (weight; height) will be summarized descriptively by participant group (BAM or Non-BAM) for the Safety population. Continuous variables will be summarized by number of participants and mean, SD, median, minimum, and maximum values. Categorical variables will be summarized by number and percentage of participants.

Abnormalities in participants' medical and surgical histories will be coded using the *MedDRA (Medical Dictionary for Regulatory Activities, version 20 or newer)*. The number and percentage of participants with abnormalities in medical and surgical histories in each system organ class and preferred term will be summarized by participant group for the Safety Population.

All prescription drugs, herbal products, vitamins, minerals, and over-the-counter medications taken within 30 days prior to the open-label treatment period will be recorded as prior medications. All medications taken after beginning open-label treatment and through the early termination or follow-up visit will be recorded as concomitant therapy. The use of all prior and concomitant medications is to be recorded on the participant's electronic case report form (eCRF) at each visit along with the reason the medication was taken.

Prior and concomitant medications will be listed by participant group with the drug names and Anatomical Therapeutic Chemical classification codes based on the data collected in the eCRF.

The World Health Organization (WHO) Drug Dictionary, version March 2017 or newer, will be used to classify prior and concomitant medications by therapeutic class and drug name.

9.0 EXTENT OF EXPOSURE AND TREATMENT COMPLIANCE

9.1 EXTENT OF EXPOSURE

Exposure to the study treatment for the Safety Population during the treatment period will be summarized for treatment duration, calculated as the number of days from the date of the first dose of study treatment to the date of the last dose of study treatment, inclusive. Descriptive statistics (number of participants, mean, SD, median, minimum, and maximum) will be presented by participant group (BAM or Non-BAM).

Patient-years, defined as exposure to the study treatment in years, will be summarized by participant group for the Safety Population.

9.2 MEASUREMENT OF TREATMENT COMPLIANCE

Dosing compliance for a specified period is defined as the number of tablets taken by a participant during that period divided by the number of tablets prescribed for the same period multiplied by 100. This information will be obtained from Study Treatment Record of the participant's electronic case report form.

Descriptive statistics for study drug compliance will be presented by participant group for each period between 2 consecutive visits, as well as for the whole treatment period (Visit 4 to Visit 5), for the Safety Population.

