Participants enrolled in the treatment period will return to the study site for study visits at Week 2, Week 4 (end-of-treatment study visit), and for a post-treatment follow-up study visit at Week 6. Telephone contacts may be made to participants in lieu of an on-site visit at Week 2. A complete schedule of activities (SoA) is provided in Section 2. Participants who discontinue from the study before the Week 4 visit should return to the study site to complete the early termination assessments as soon as possible after stopping the study drug.

During the open-label treatment period, participants will record via the eDiary their daily IBS-D symptoms including stool consistency (BSFS), worst abdominal pain, abdominal bloating, bowel movement frequency, rescue medication usage, number of episodes of urgency in a day, and number of episodes of fecal incontinence, if any.

The actual eDiary data entered by the participants will not be provided to the investigative site staff at any time during the study to prevent any potential bias in subsequent participant entries. However, periodic notifications will be generated to inform the investigator of participants' ongoing compliance with eDiary entries and to alert investigators if participants have experienced episodes of constipation or have required excessive loperamide rescue medication for acute treatment of uncontrolled diarrhea.

The total duration of the study is up to 11 weeks, which includes: screening period (0-2 weeks), pretreatment period (2-3 weeks), 4-week open-label treatment period, and 2-week post-treatment follow-up period. A total of 6 study visits are planned for each participant:

- Screening, Week -3 to -5 (Visit 1) prior to Baseline visit
- Pretreatment, Week -3 to -2 (Visit 2) prior to Baseline visit
- Day 1 (Visit 3; first administration of study drug)
- Week 2 (Visit 4; Week 2 of treatment), may be done by telephone
- Week 4 (Visit 5; end of treatment/early termination)
- Week 6 (Visit 6; post-treatment follow-up)

The study design is presented in [Table 5-1](#).

Table 5-1 Study Design

Period	Screening ^a	Pretreatment ^a	Open-Label Treatment			Post-Treatment
Duration	0-2 weeks	2-3 weeks	4 weeks			2 weeks
Week	Screening	Pretreatment	Baseline	Week 2 ^b	Week 4 (EOT/ET)	Week 6 ^b (Follow-up)
Study Visit	1	2	3	4	5	6
Study Day			1	15 (± 2)	29 (± 2)	Visit 5 + 14 days (± 7)

7 α C4 = 7 α -hydroxy-4-cholesten-3-one; BA = bile acid

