7.6. Treatment Compliance

Treatment compliance will be assessed at the study site by pill counts. This review will be documented in the source documents.

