16.0 DATA HANDLING CONVENTIONS

16.1 VISIT TIME WINDOWS

Table 16.1–1 presents the visits assigned for efficacy and safety analyses and the corresponding range of treatment days (window) during which an actual visit may occur.

Table 16.1–1. Visit Time Windows

Derived Visit	Scheduled Visit Day^a	Window
Visit 1 (Screening)		
Visit 2 (Pre-treatment)		
Visit 3 (Baseline)	Day 1	Days \leq 1
Visit 4	Day 15	Days [2, 21]
Visit 5 (End of Treatment ^b)	Day 29	Days \geq 22 and last dose day +1
Visit 6	Day 33	Days \geq last dose day + 2

a Relative to the date of the first dose of treatment period. Day 1 = the date of the first dose of study treatment. There is no Day 0.
b Presented in analysis tables for safety parameters, including but not limited to clinical laboratory values and vital signs.

If the assessment date (if the assessment date is unavailable, use visit date instead) is on or after the date of the first dose of study treatment, the study day is calculated by assessment date – date of the first dose of study treatment + 1. If the assessment date is before the date of the first dose of study treatment, the study day is calculated by assessment date – date of the first dose of study treatment. Therefore, a negative day indicates a day before the start of the study treatment.

If a participant has 2 or more visits within the same window, the last visit with a non-missing value will be used for analysis.

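### SAP 9.2 sets the whole treatment period for compliance at Visit 4 to Visit 5, although dosing starts at Visit 3, so the overall line covers nominally 14 of 28 days

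*SAP*

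**What the plan says.** SAP 9.2 defines compliance for a period as tablets taken divided by tablets prescribed in that period, times 100. It takes the data from the study treatment record in the eCRF and asks for summaries in each cohort, "for each period between 2 consecutive visits, as well as for the whole treatment period (Visit 4 to Visit 5), for the Safety Population".

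The visit calendar appears in several places, and they agree with one another:

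- SAP 4.0 describes "a 4-week open-label treatment period during which time participants will receive eluxadoline 100 mg BID" and lists the visits as "Day 1 (Visit 3; first administration of study drug); Week 2 (Visit 4; Week 2 of treatment" and so on, with Visit 5 at Week 4 as the end-of-treatment or early-termination visit.
- Protocol 5.1 lists "Day 1 (Visit 3; first administration of study drug" in the same way. Its Table 5-1 gives Visit 4 as Day 15 (± 2) and Visit 5 as Day 29 (± 2).
- Protocol 9 has study treatment dispensed on Day 1 (Visit 3).
- SAP 16.1 anchors study days to the first dose: "Day 1 = the date of the first dose of study treatment. There is no Day 0".
- SAP 9.1 counts exposure from first dose to last dose, inclusive.

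**The concern.** The label and the visits in the parenthesis cannot both be right, because treatment is already about two weeks old at Visit 4. A programmer who follows the parenthesis would report second-half compliance under a whole-period label. That has three consequences.

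1. The overall line adds nothing. The sentence already asks for each interval between consecutive visits, and Visit 4 to Visit 5 is one of them. No true overall compliance would be reported.
2. A Safety Population participant who stops before Visit 4 has no dosing in the interval and so no usable overall value. Such stops are foreseeable: Protocol 3.3 reports that about half of constipation events came in the first 2 weeks, and Protocol 8.1 makes severe constipation a reason for mandatory discontinuation.
3. The interval lines may not always fill the gap. Protocol 7.6 says "Treatment compliance will be assessed at the study site by pill counts", while Protocol 5.1 says "Telephone contacts may be made to participants in lieu of an on-site visit at Week 2". Where Visit 4 was a call, there may be no count with which to split the tablets.

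Exposure (SAP 9.1) and overall compliance (SAP 9.2), two neighbouring summaries of the same population, would also cover different spans.

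**Working it through.** **Inputs.** First dose on Day 1 at Visit 3 (SAP 4.0, Protocol 5.1). Visit 4 on Day 15 ± 2 and Visit 5 on Day 29 ± 2 (Protocol Table 5-1). Treatment lasts 4 weeks (SAP 4.0). One tablet is taken twice daily (Protocol 7.1). Each cohort has 12 participants. Assumption: dosing runs from Day 1 to Day 28.

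**Reproducing the stated treatment length.** Visit 3 to Visit 5 = 29 − 1 = 28 days = 4 weeks, which matches. The total is 2 × 28 = 56 tablets.

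**Coverage of the literal rule.** Visit 4 to Visit 5 = 29 − 15 = 14 days, which is half of 28. Tablets from Visit 4 to Day 28 = 2 × (28 − V4 + 1), where V4 is the day of Visit 4.

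**Error in the overall line.** Let *f* be the share of tablets covered, *e* compliance before Visit 4 and *l* compliance from Visit 4 on.

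- True overall compliance = (1 − f)·e + f·l
- Reported value = l
- Error = l − [(1 − f)·e + f·l] = (1 − f)·(l − e)

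| Visit 4 on | Tablets covered | f | Error per 10-point gap (l − e) |
|---|---|---|---|
| Day 13 | 2 × 16 = 32 of 56 | 57.1% | 0.429 × 10 = 4.3 points |
| Day 15 | 2 × 14 = 28 of 56 | 50.0% | 0.500 × 10 = 5.0 points |
| Day 17 | 2 × 12 = 24 of 56 | 42.9% | 0.571 × 10 = 5.7 points |

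The sign follows that of l − e. The table holds dosing at 28 days. If Visit 5 also moves by ± 2 days and calendar days are counted, the covered share runs from 10/26 = 38% (Visit 4 on Day 17, Visit 5 on Day 27) to 18/30 = 60% (Days 13 and 31).

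**Illustration with assumed values.** Compliance of 60% in Weeks 1–2 and 100% in Weeks 3–4 is truly 80% overall; the literal rule reports 100%. The reverse pattern is also truly 80%, and the rule reports 60%.

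**Cohort level.** One participant with a 10-point gap moves the mean of 12 by 5.0/12 = 0.42 points. One participant who stops before Visit 4 leaves 1/12 = 8.3% of a cohort without an overall value.

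**The case against.** The strongest counter-argument is that visit labels have a second meaning in the SAP. Section 16.1 assigns Days 2–21 to Visit 4 and days from 22 to the end of treatment to Visit 5. If the parenthesis means those two windows taken together, it runs from Day 2 to Day 28, or 27 of 28 days, and almost nothing is lost. But SAP 9.2 does not refer to the windows. It speaks of periods lying between consecutive visits, which treats visits as points in time; adjoining windows have no period between them. Nothing suggests the window reading was intended, and it would still drop Day 1.

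A related objection concerns early stoppers. Visit 5 is also the early-termination visit, so such a participant may well have a final count. Under the 16.1 windows, however, a visit on Days 2–21 falls in the Visit 4 window. Some of these visits also meet the Visit 6 rule: a visit on Day 10 after a last dose on Day 5 satisfies both. How they would be handled depends on a program that cannot be seen. What holds without the windows is simpler: someone who stopped before Visit 4 was not taking tablets between Visits 4 and 5.

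It is also fair to say that the Visit 3 to Visit 4 line would report the first half wherever a Visit 4 count exists. Where none exists, a Visit 4 to Visit 5 figure could not be calculated from pill counts either. The telephone point therefore remains a possibility only, since the schedule of activities is not readable in the text available. The 10-point gap is a unit chosen for illustration, not an expected value. Finally, table specifications sit in a separate document, so the program may already use the right visits. These points limit the harm; they do not reconcile the parenthesis with the visit calendar.

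**Conclusion.** The concern holds. SAP 9.2 contradicts the visit calendar in both documents, and no other section corrects it; SAP 17.0 declares no changes from the protocol, so a Visit 4 start is not an announced choice. It is probably a slip in one visit number.

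The half-period coverage assumes that visits are points in time and that dosing runs from Day 1 to Day 28. The size of any error in the reported figure is unknown without compliance data, and its direction depends on whether early or late dosing was worse. The consequence is limited: the summary is descriptive, exposure and disposition are tabulated separately, and no analysis population or efficacy endpoint uses compliance. Wrong as written, minor, and worth correcting because the literal rule yields a mislabelled figure.

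**What to change.** In SAP 9.2, change the parenthesis to Visit 3 (Day 1) to Visit 5/ET. Defining the span as first dose to last dose would do the same job, would match SAP 9.1, and would avoid any dependence on how the 16.1 windows classify an early-termination visit. Keep the between-visit summaries as they are, and check that the table program uses the corrected span.

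The cost is one visit number and a check of one program. No new data are needed: tablets are dispensed on Day 1, and a site count at Visit 5/ET would cover the whole period without a Visit 4 count. The reported overall value may rise or fall as a result.
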